### **Project significance and future perspectives**

The project includes; 1) Identifying biomarkers in acutely ill older patient groups associated with length of hospital stay, non-elective readmissions, muscle mass, muscle strength, frailty, and time to mortality within 90 days. 2) Combining biomarker measurements with clinical and functional measurements for predicting loss of muscle mass and function

during hospitalization in geriatric patients, and investigating the association with hospital length of stay, non-elective readmissions, time to mortality, frailty, and discharge to a higher level of care. The findings of the study will not only have implications for geriatric patients but has the potential to be translated across disciplines to any patient at risk of hospital induced muscle wasting.

## **Subjects and methods**

### **Subjects**

Acutely ill medical patients (age > 65 yrs) for WP1 (n=1100) will be enrolled ad hoc from Bispebjerg-Frederiksberg Hospital.

Geriatric patients (age > 65 yrs) for WP2 (n=200) will be enrolled ad hoc from Bispebjerg-Frederiksberg Hospital.

For both WP1 and WP2 we aim to include patients with a dementia diagnosis and patients with delirium, as this group of patients represent a large portion of the elderly patients admitted to the hospital. Thus, the project aims to be representative of the general elderly patient population. Patients with dementia will be identified through patient journals. Depending on the severity of dementia and delirium, it might be possible that some patients are unable to sign participant consent, and in these cases, we will seek participant consent from a close relative or guardian. Independent medical doctors who have knowledge of the project but are not associated with the project and are independent to the interests of the principal investigator will evaluate whether these subjects are able to participate in the study. The medical doctors designated to perform this evaluation is chosen based on available independent doctors on duty in the department that day. Two large prospective cohort studies have previously reported that dementia is independently associated with frailty (69,70). Another study has shown that frail patients have an increased risk of developing delirium and that frail patients with delirium have a reduced survival rate following hospitalization compared to non-frail patients with delirium (71). This puts this specific patient population at increased risk of adverse outcomes and muscle wasting during hospitalization. As such, it is essential that we increase our knowledge of the underlying mechanisms and predictors of muscle wasting and the predictors of longer hospital stays and mortality in this specific patient population so that we might help future

patients with dementia and delirium. The project entails minimal discomfort for the subjects and has no permanent side effects. Should the patients with delirium regain their legal competency during their hospital stay, they will have to sign an independent participant consent.

All subjects will have blood tests performed to evaluate levels of GDF11 & GDF15, inflammatory cytokines and acute-phase proteins, sex hormones and immune activity (suPAR). In addition, all subjects will have their hand-grip strength, chair-rise ability and body composition (BIA) assessed. Their frailty score and risk of pressure ulcers will be assessed by the CHSA Clinical Frailty Scale and Braden score, respectively. The Charlson Comorbidity Index will be used to assess comorbidity, SARC-F will evaluate the presence of sarcopenia and the Orientation-Memory-Concentration test (OMC) will evaluate cognitive function in all subjects

Subjects included in WP2 will have an additional geriatric assessment including the Barthel Index and De Morton Mobility Index (DEMMLI), which are already part of standard clinical practice. Functional status will additionally be evaluated by a gait-speed test.

### **Information from patient records and other data sources**

Prior to obtaining participant consent we will need access to the summary in patient records when dementia is suspected. This is solely to confirm the dementia diagnosis as these patients will need to be evaluated by an independent physician to determine whether they are able to participate in the study.

After obtaining participant consent, direct access to information from patient records and/or the National Patient Registry (NPR) is necessary for project implementation and to control for confounders and covariates in analyses. Participants will be informed of this in the participant information sheet. This information is disclosed to the investigator and includes information regarding:

- age, height and weight
- smoking habits
- results of routine bloodwork
- admission to the intensive care unit
- Early Warning Score (EWS)

- disease history and the number of ICD-10 discharge diagnoses 5 years prior to admission, to assess comorbidity
- discharge to a higher level of care (WP2)
- hospital length of stay
- readmissions within 90 days in the region on Zealand and Capital region of Denmark
- number of hospitalizations (acute and elective) 1 year prior to admission
- number of medications prescribed at admission, to evaluate polypharmacy
- results of bloodwork associated with the project
- results from questionnaires (Barthel Index, OMC, SARC-F, DEMMI, Braden Score & CSFA Clinical Frailty Scale)

Information regarding patient mortality within 90 days of admission will be extracted from the Danish Civil Registry System.

The participant consent will give the investigators as well as possible supervisory authorities access to obtain information from patient records to view health information necessary for the implementation of the project, as well as required quality-control and monitoring.

### **Processing of personal information**

All participant data are confidential, are subject to confidentiality and will be handled in compliance with the law on the processing of personal information. Results from participants will be published in scientific journals, securing the complete anonymity of participants. All procedures will be conducted according to “Good Clinical Practice” standards, regarding initiation, monitoring and reporting. All protocols will be submitted for approval by the local ethics committee and Danish Data Protection Agency before trial-initiation and the project will comply with the regulations of the General Data Protection Regulation (GDPR) and the Data Protection Act.

## **Recruitment and participant consent**

All acutely ill old medical patients (>65 years) are included in the project. Initial contact to the patients will be made immediately after admission to Bispebjerg-Frederiksberg Hospitals, by research personnel directly associated with the project. Initial contact will entail informing the eligible participants, that a scientific study is being conducted and that they have the possibility to take part in it. Interested participants will be given the written participant information and we will set up a meeting immediately or within the following hours for the verbal information. Interested participants will be informed that they have the right to bring an assessor to the meeting.

In the case of severe dementia or delirium, it might be possible that some patients are unable to sign participant consent, and in these cases, we will seek participant consent from a close relative or guardian, should the guardianship include access to signing participant consent in research. Independent medical doctors who have knowledge of the project but are not associated with the project and are independent to the interests of the principal investigator will evaluate whether these subjects are able to participate in the study, and if so, they will also sign the participant consent. The medical doctors designated to perform this evaluation is chosen based on available independent doctors on duty in the department that day. Interested participants and their relatives or guardian will be given the written participant information and we will set up a meeting immediately or within the following hours for the verbal information. The verbal information will be adjusted to fit the patient's cognitive abilities.

The verbal information will be given by research personnel directly associated with the project. The meeting will take place in the hospital room to ensure that the conversation is as undisturbed as possible, and this will give eligible participants, relatives or guardians time to listen and ask questions. The verbal information will be understandable without the use of technical terms and will be based on the written participant information including aim, methods, possible risks and side-effects and disclosure of personal information. Possible participants, relatives or guardians will be given time to consider whether they would like to participate in the study before signing a participant consent. Should the patients with delirium regain their legal competency during their hospital stay, they will have to sign an independent participant consent.

The appendix “Forsøgspersoners rettigheder i et sundhedsvidenskabeligt Forskningsprojekt” will be enclosed with the written information and reviewed during the verbal information.

Following the written and verbal information, all participants will be informed of any newly discovered risks, side effects or any essential changes in study design. Participants will also be informed if the study is terminated and the reasons for termination.

### **Inclusion criteria**

All acutely ill medical patients aged 65+ years admitted to Bispebjerg-Frederiksberg Hospital.

### **Exclusion criteria**

Exclusion criteria includes being under the age of 65 years, terminal illness, droplet or airborne isolation, patients who do not understand Danish and patients with temporary civil person registration numbers (CPR).

### **Statistical considerations**

The current study will recruit participants during a 1-year period to avoid any seasonal differences in the patient population. The acute medical unit receives approximately 10-20 patients a day over the age of 65, giving a total of roughly 5475 patients a year. We estimate a participation rate of 20% due to unwillingness to participate, inability to perform measurements or cognitive impairments or delirium affecting their ability to sign participant consent. We aim to include a total of roughly 1100 participants, of which 200 patients are admitted to the geriatric rehabilitation care unit.

### **Overall outcome analysis**

To test whether clinical, functional and biological biomarkers are associated with length of stay we will perform multivariate logistic regression and to test whether clinical, functional and biological biomarkers are associated with loss of muscle mass and function we will perform multivariate linear regression. To evaluate the prognostic abilities of biomarkers (individual, in combination and combined with clinical and functional measures) we will use area under the curve for receiver operating characteristics (AUROC) statistics.

Table of summary statistics will be presented with a number of baseline variables (age, sex, functional measures, results of blood tests, comorbidities).

Continuous variables will be summarized with: n (non-missing sample size), mean, standard deviation, median, interquartile range, number of missing values. Categorical variables will be reported as frequency and percentages (based on non-missing sample size) and number of missing values.

Continuous and ordinal variables will be tested by Wilcoxon analysis for differences between groups. Categorical variables will be tested with chi-square. Missing data will be imputed.

A reference group of 2058 patients over the age of 65 from Bispebjerg-Frederiksberg University Hospital and Herlev-Gentofte Hospital had a mean age of 78.3 years and a mean length of stay of 5.8 days during hospitalization. 817 of these patients (39.7%) had a prolonged length of stay, defined as a hospitalization lasting more than 96 hours.

With a sample size of 1100 and the assumption that approximately 40% of old medical patients have a prolonged hospital stay, an AUROC of 82 will have a power of 0.9 and a significance level of 0.05. The primary outcome will be mean length of stay. Patients will be grouped in either normal or extended length of stay (<96 hours) and Cox regression analysis will be used to compare differences in readmission and mortality. To assess the discriminative ability of biomarkers with regards to extended length of stay, we will use the area under the curve (AUC) for receiver operating characteristics (ROC) curves. AUCs for different ROC curves will be compared using the DeLong test.

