**The specific aims of the present project are therefore to:**

- I. Examine whether the level of a variety of biomarkers at admission are associated with length of hospital stay, time to first readmission within 90 days, and time to mortality within 90 days in old patients, and whether the combination of clinical and functional measures with these biomarkers can identify patients at risk of prolonged hospital stay, readmissions and mortality. Primary end-point is length of stay. Secondary end-points are time to first readmission, time to mortality, muscle mass, muscle strength and frailty score (WP1).
- II. Establish biomarker assays for predicting muscle loss and loss of function in old patients hospitalized at a geriatric ward, assessing whether levels of a variety of biomarkers combined with clinical and functional measures are associated with length of hospital stay, readmissions, mortality and whether patients are discharged to a higher level of care. Primary end-points are the relative change in muscle mass, muscle strength and muscle function. Secondary end-points are length of stay, time to first readmission, time to mortality, frailty score and discharge to a higher level of care (WP2)

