The knowledge surrounding the prevalence and determinants of sarcopenia in geriatric rehabilitation care is scarce, and it is unknown whether specific biomarkers can predict physical deconditioning during hospitalization. As such, the development of novel interventions for this group of patients is hampered by the lack of understanding of the basic biological mechanisms driving sarcopenia in conjunction with other age-related diseases in humans. The importance of sarcopenia has recently been underlined by its inclusion as a reportable disease in the Centers for Diseases Control and Prevention (ICD-10-CM code M62.84) in October 2016 (31). However, despite the serious consequences of sarcopenia being widely recognized, the diagnose has yet to be implemented in clinical practice in Denmark. Lack of knowledge and systematic assessment hinders diagnosis and treatment of sarcopenia and leads to physical deconditioning during hospitalization. Consequently, more than 50% of geriatric patients report a decline in functional capacity after discharge, often leading to a need for prolonged and expensive rehabilitation interventions (8).

As successive events of hospitalisation have been suggested to contribute to the development of sarcopenia, and even short periods (4-5 days) of skeletal muscle disuse are known to induce muscle atrophy (9,10), we have defined a prolonged hospital length of stay as an admission lasting >96 hours. In addition, we have defined patients discharged to a higher level of care as patients receiving increased relief, patients with increased need for a caregiver, patients referred to rehabilitation or 24-hour care, or patients moving to a nursing home following discharge. Readmission data will be limited to readmissions in the region of Zealand and the Capital Region of Denmark.

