## **RESEARCH PLAN**

This project includes 2 work packages (WP), of which WP1 is a prospective cohort study of acutely ill older patients (65+ years) referred to the hospital and will investigate the association of biomarkers combined with clinical and functional measures with length of hospital stay, time to first non-elective readmission, muscle mass, muscle strength, frailty, and time to mortality. WP2 is a prospective cohort study of older patients (>65 years) admitted to a geriatric ward for treatment of the acute disease and rehabilitation care and will investigate the possible association of biomarkers with the relative change in muscle mass and function, frailty score, length of hospital stay, time to first non-elective readmission, time to mortality and discharge to a higher level of care. Readmission data will be limited to readmissions in the region of Zealand and the Capital Region of Denmark.

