### **WP1: Biomarkers in the acutely ill older patient**

**Hypothesis:** We hypothesize that combining clinical and functional measures with systemic biomarkers has the potential to identify older acutely ill medical patients at risk of prolonged (>96 hours) hospital stays, non-elective readmissions, and mortality.

**Overview of Actions:** Acutely ill medical patients (age >65 years) referred to Bispebjerg-Frederiksberg Hospital will consecutively be enrolled in the study. We will recruit participants during a 1-year period.

**Assessments:** Blood tests, frailty (CSHA Clinical Frailty Scale), risk of pressure ulcers (Braden Score), sarcopenia (SARC-F), hand-grip strength, chair-rise test and body composition (BIA). Blood samples will be used to assess biomarkers of muscle atrophy and wasting (GDF-11 & GDF-15), inflammatory cytokines and acute-phase proteins, sex hormones and immune activation (suPAR). All assessments will be performed within the

first 24 hours of admission. Primary endpoint is length of hospital stay. Secondary endpoints are time to first non-elective readmission, time to mortality, muscle strength, muscle mass and frailty.

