### **WP2: Biomarkers for changes in muscle mass and function in geriatric patients**

**Hypothesis:** We hypothesize that combining clinical and functional measures with biomarkers will give us the opportunity to elucidate a composition of biomarkers associated with the change in muscle mass and function during hospitalization, thus having the potential to identify future geriatric patients at risk of physical deconditioning and prolonged (>96 hours) hospital stays, non-elective readmissions, mortality, and discharge to a higher level of care.

**Overview of Actions:** Geriatric patients (age >65 years) referred to geriatric rehabilitation care at Bispebjerg-Frederiksberg Hospitals will be enrolled in the study. We will recruit participants during a 1-year period.

**Assessments:** Included patients will be monitored by blood tests immediately following admission and at discharge. A geriatric assessment will be performed during admission (Barthel Index, the CSHA Clinical Frailty Scale, SARC-F, the Orientation-Memory-Concentration test (OMC) and De Morton Mobility Index (DEMMI). Measurements of muscle function (e.g. hand-grip strength, gait-speed and sit-to-stand tests) and body composition (BIA) will be performed shortly after admission and at discharge. Blood samples will be used to assess biomarkers of muscle atrophy and wasting (GDF-11 & GDF-15), inflammatory cytokines and acute-phase proteins, sex hormones and immune activation (suPAR). Preliminary assessments will be performed within the first 24 hours of admission. Primary end-points are relative change in muscle mass, muscle strength and muscle function. Secondary end-points are length of hospital stay, time to first non-elective readmission, time to mortality, frailty, and discharge to a higher level of care.

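### Cox regression is written only for length-of-stay groups, so the biomarker questions on time to readmission and death have no time-to-event model; a clock started at admission would also bias the stay-group mortality comparison downward

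*Combined protocol and SAP*

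**What the plan says.** **The questions.** Aim I is to "Examine whether the level of a variety of biomarkers at admission are associated with length of hospital stay, time to first readmission" and time to death, both within 90 days. The section RESEARCH PLAN repeats this for WP1 as the "association of biomarkers combined with clinical and functional measures with length of hospital stay, time to first non-elective readmission" and further endpoints. The WP1 section states: "Secondary endpoints are time to first non-elective readmission, time to mortality, muscle strength, muscle mass and frailty". The WP2 section states: "Secondary end-points are length of hospital stay, time to first non-elective readmission, time to mortality, frailty, and discharge to a higher level of care".

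**The analyses.** Overall outcome analysis assigns logistic regression to length of stay and linear regression to loss of muscle mass and function. It assigns AUROC to the prognostic ability of biomarkers, without naming an outcome in that sentence. Where it does name an AUC outcome, the outcome is extended stay. Cox regression appears once, directly after patients are divided by stay: "Cox regression analysis will be used to compare differences in readmission and mortality".

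**The group and the windows.** The background section on sarcopenia says "we have defined a prolonged hospital length of stay as an admission lasting >96 hours". The section on patient records and other data sources says "Information regarding patient mortality within 90 days of admission will be extracted". For readmission it lists only "readmissions within 90 days in the region on Zealand and Capital region of Denmark", with no start of the window. No Cox time origin, landmark, time-dependent term, competing-event rule or rule for deaths before 96 hours is given.

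**The concern.** There are two linked problems.

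1. The exposure in the only Cox analysis is the stay group. That comparison cannot answer whether an admission biomarker is associated with time to readmission or time to death. The exposure terms and time origin for two secondary endpoints in both work packages would then be chosen after the data are seen.

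2. The stay group is known only once 96 hours have passed. A patient in the extended group cannot, by definition, have died in hospital before then. With follow-up from admission, the first 96 hours are death-free for the extended group and hold all the early deaths of the normal group. The hazard ratio for extended against normal stay is then too low whatever the truth, and a real excess risk in long stayers is understated with loss of power.

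**Working it through.** **Plan figures.** Prolonged stay in the reference group: 817/2058 = 39.7%, as stated. Mean stay is 5.8 days and the planned sample is 1100. The plan's only power statement concerns an AUROC, so it has no Cox figure to reproduce.

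**Assumptions not in the documents.** 90-day mortality *M* of 10–20%. Share *f* of those deaths in the first 96 hours: about 5%, 10% or 20%. A constant hazard gives *f* = [1 − (1 − *M*)^(4/90)]/*M*, which is 4.7% at *M* = 10% and 4.9% at *M* = 20%.

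**Hand calculation.** Let *q* = 0.397 be the share of long stays and θ the true hazard ratio.
- Long stayers' share of deaths: *s* = θ*q*/(θ*q* + 1 − *q*).
- With an admission clock, the early part of that share is counted as normal stay, so the extended group's observed share is *p* = (1 − *f*)*s*.
- Estimated hazard ratio ≈ [*p*/(1 − *p*)] / [*q*/(1 − *q*)], with *q*/(1 − *q*) = 0.397/0.603 = 0.658. This treats the extended share of the risk set as constant at *q*.

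For θ = 1, *s* = 0.397. For θ = 1.5, *s* = 0.5955/1.1985 = 0.497.

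| *f* | *p* (θ = 1) | HR (θ = 1) | *p* (θ = 1.5) | HR (θ = 1.5) |
|---|---|---|---|---|
| 5% | 0.377 | 0.92 | 0.472 | 1.36 |
| 10% | 0.357 | 0.84 | 0.447 | 1.23 |
| 20% | 0.318 | 0.71 | 0.398 | 1.00 |

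**Simulation.** Stay was lognormal, fitted to the mean of 5.8 days and 39.7% above 4 days (log-SD 1.16, median 2.95 days). The death hazard was piecewise constant before and after 96 hours, and the group was set by observed stay. With no true effect the Cox hazard ratio was about 0.92, 0.84–0.85 and 0.71. A true 1.5 became 1.35–1.37, about 1.23 and about 1.00. Overall mortality hardly mattered; the early share drives the result. A 96-hour landmark returned 0.99–1.01 for a true 1 and 1.49–1.51 for a true 1.5.

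**Effect on inference, constant hazard, *n* = 1100.** With no true effect, false positives were 6–9%. With a true 1.5, power was 41–68% from admission and 63–88% with the landmark.

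**Readmission.** A patient still in hospital cannot be readmitted. With 20–30% readmission assumed, no deaths and no true difference, the hazard ratio was about 0.88 if time ran from admission (0.93–0.95 with a narrower stay distribution) and 1.00–1.01 from discharge.

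**What the missing biomarker model could show.** The hazard ratio per SD detectable with 80% power, unadjusted, is exp[(1.96 + 0.84)/√deaths]. WP1 with 110–220 deaths (10–20% of 1100) gives 1.31–1.21. WP2 with 20–40 deaths (the same rates assumed for *n* = 200) gives 1.87–1.56.

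**The case against.** The strongest reply has four parts.

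- **The Cox sentence joins two clauses.** Grouping by stay is also needed for the AUC analysis that follows, so Cox regression need not be confined to that contrast. The tied reading is the more natural one. On the looser reading the model family is named but the exposure is still missing.
- **The AUROC sentence does not restrict the outcome.** It could cover 90-day readmission and death as yes/no outcomes. That is fair, and it serves part of the aim of identifying patients at risk. It is not an analysis of time to event.
- **The bias is conditional.** No aim treats length of stay as an exposure for death or readmission, and the window from admission describes data extraction, not a Cox origin. This stands. Admission is the natural clock for mortality, not a stated one.
- **The sizes rest on assumed early-death shares.** This also stands. Excluding terminal illness, and enrolling after admission, favour the low end.

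A reader might infer more than the documents support:
- That the plan has no survival method for these endpoints. It does name Cox regression.
- That long stay would appear protective. With a true hazard ratio of 1.5 the estimate stays above 1 at early shares of 5% and 10%, and is about 1.00 at 20%.
- That the readmission comparison is biased as written. Its window has no stated start, and the simulation shows the problem only when time runs from admission.
- In the other direction, that the primary length-of-stay analysis is untouched. With no rule for early deaths, a patient who dies before 96 hours is coded as normal stay there too.

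**Conclusion.** The gap in the text is firm: no time-to-event model with a biomarker term is assigned to readmission or mortality, and neither Cox clock is stated. The direction of the mortality bias is also firm if time starts at admission and no landmark or time-dependent term is used. Its size is a judgement. The hazard ratio under no effect is lowered by about 8% if about 5% of 90-day deaths are early, by 15–16% at 10%, and by about 29% at 20%. The bias is probably modest, but at the upper end it would hide a true hazard ratio of 1.5. The point should be fixed before analysis. It concerns secondary endpoints and a side comparison, so it does not undermine the study as a whole.

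**What to change.** 1. **Add the biomarker models.** Specify Cox models with admission biomarkers, alone and with the clinical and functional measures.
   - Death: time zero at blood sampling, or at admission with delayed entry, to day 90 from admission.
   - First non-elective readmission: from live discharge, with death as a competing event and the 90-day window stated. Say that this conditions on survival to discharge. Aim I omits the non-elective qualifier that the later sections use; align them.
   - WP2: report estimates with confidence intervals and few covariates.
2. **Repair the stay-group comparison, if kept.** Use a 96-hour landmark, or a time-dependent stay term, for mortality, and discharge as time zero for readmission.
3. **State how deaths before 96 hours are handled** wherever stay is dichotomised, including the primary logistic and AUC analyses.
4. **Minor wording.** Fix a short covariate list in advance; none is given for the logistic or linear models either. Reconcile the bracketed label, which reads as less than 96 hours, with the definition of more than 96 hours.

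**Cost.** SAP wording and a little extra analysis. The landmark leaves out deaths before 96 hours: 5–15 of 1100 under a constant hazard, and with no true effect 1100 × 0.20 × 0.20 = 44 if mortality is 20% and a fifth of deaths are early. A time-dependent term keeps them. Starting readmission at discharge leaves out in-hospital deaths. No new data are needed if follow-up is censored at day 90 from admission.
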